#### **4.2.3.6 Supplementary Analyses of the Secondary Endpoint #1**

Not Applicable.

#### **4.2.3.7 Subgroup Analyses**

Subgroup analyses will be performed using separate Cox models, as per section 4.2.3.4, by age (18-64, 65-84 and over 85 years), sex (female, male), recruitment country (France,

Italy, Spain, UK, Belgium and Netherlands), presence of heart failure (Yes/No, identified per Medical History using an SMQ of “Cardiac Failure”; SMQ Code: 20000004), diabetes (Yes/No, identified per Medical History eCRF using a PT of “Type 2 diabetes mellitus”), RAASI use at screening (Yes/No, identified per Concomitant Medication eCRF as CMCLASCD in (‘C09AA’, ‘C09BA’, ‘C09BB’, ‘C09BX’, ‘C09CA’, ‘C09DA’, ‘C09DB’, ‘C09DX’, ‘C09XA’) where Start Date is prior to date of informed consent), CKD stage, without diagnosis of CKD (but eGFR  $<90 \text{ ml/min/1.73m}^2$ ), baseline  $K^+$  ( $5.0 < K^+ \leq 5.5$  versus  $5.5 < K^+ \leq 6.5 \text{ mmol/L}$ ), an alternative baseline  $K^+$  categorisation ( $5.0 < K^+ \leq 5.5$ ,  $5.5 < K^+ \leq 6.0$ , and  $6.0 < K^+ \leq 6.5 \text{ mmol/L}$ ) and by duration of index hospitalisation ( $<7$  days versus  $\geq 7$  days hospitalisation during the inpatient phase). Subgroup analyses will only be conducted providing there are 10 or more events per subgroup category.

#### **4.2.4 Secondary Endpoint #2 (All-cause Hospital admission or ED visit with HK)**

*Time to first occurrence of any component of all-cause hospital admission or ED visit with HK as a contributing factor at any time post-discharge up to 180 days.*

##### **4.2.4.1 Definition**

- Population: Full analysis set
- Endpoint: Time to first occurrence of either component of the composite outcome at any time post-discharge up to 180 days.
- Intercurrent event strategy: Participants who discontinue treatment or who have ED visit without HK as a contributing factor will continue to be followed up to the first component of the composite endpoint (treatment policy strategy). Participants who die of any cause, use rescue therapy for HK or are lost to follow-up will be censored at the date of death, use of rescue therapy or loss to follow-up respectively. Participants who have RAASI down-titration (including discontinuation) will continue to be followed up to the first component of the composite endpoint (treatment policy strategy). Participants who do not have an event by 180 days post-discharge will be administratively censored at the date of 180 days post-discharge.
- Population level summary (analysis): Kaplan-Meier plots of the survival function for the SZC and SoC treatment groups will be presented. Log-rank test for testing will be used to calculate a two-sided p-value, Cox proportional hazards ratio for estimation, with randomised treatment group (reference level SoC) as the independent variable. The HR and the two-sided 95% confidence interval will be presented. The risk difference and two-sided 95% confidence interval will be presented (as per section 4.2.3.2) at 180 days post-discharge.

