**Table 5: Testing order for primary and secondary efficacy endpoints**

Order	Efficacy Endpoint	Section
1	Occurrence (yes/no) of normokalaemia (NK) ( $K^+$ between 3.5 and 5.0 mmol/L, inclusive) at 180 days post-discharge	4.2.2
2	Time to first occurrence of all-cause hospital admission or ED visit with HK as a contributing factor, or all-cause death, or use of rescue therapy for HK at any time post-discharge up to 180 days inclusive.	4.2.3
3	Time to first occurrence of all-cause hospital admission or ED visit with HK as a contributing factor at any time post-discharge up to 180 days inclusive.	4.2.4
4	Number of all-cause hospital admission or ED visits with HK as a contributing factor, at any time post-discharge up to 180 days.	4.2.5
5	Time to first occurrence of RAASI down-titration (or discontinuation) at any time post-discharge up to 180 days.	4.2.6
6	Time to first occurrence of hospital admission or ED visit, both with HK as a contributing factor at any time post-discharge up to 180 days.	4.2.7
7	Number of hospital admission or ED visits, both with HK as a contributing factor, at any time post-discharge up to 180 days.	4.2.8

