#### 4.2.2.5 Sensitivity Analyses of the Primary Endpoint

The analyses of the primary endpoint will be repeated as per section 4.2.2.4 but with alternative modelling:

- Population level summary (analysis): Providing there are sufficient participants within each covariate to support the analysis, the logistic regression model will include randomised treatment group and the following baseline variables: age (as a cubic spline), sex (male/female), participant recruitment country, presence of heart failure (yes/no), diabetes (yes/no), RAASi use (yes/no), CKD stage and baseline  $K^+$  ( $5.0 < K^+ \leq 5.5$  versus  $5.5 < K^+ \leq 6.5$  mmol/L) as independent variables. Sufficient participants for a covariate to be included will be considered if there are more than 10 participants with an event in each level of the covariate.

The analyses of the primary endpoint will be repeated as per section 4.2.2.4 but the estimand will be varied:

- Intercurrent event strategy: As primary estimand, but participants needing rescue therapy for HK will follow the treatment policy strategy (i.e., regardless of the intercurrent event).
- Intercurrent event strategy: As primary estimand, participants with RAASi down-titration (including discontinuation) will follow the treatment policy strategy (e.g. regardless of the intercurrent event).
- Intercurrent event strategy: As primary estimand, but participants who die or are lost to follow-up prior to 180 days post-discharge will not be evaluated (completers analysis only).
- Hypothetical strategy: As primary estimand, but participants who are lost to follow-up after 90 days (visit 7) or who are missing  $K^+$  status at 180 days will have their  $K^+$  status at 90 days, if available, carried forward to 180 days and included in the analysis using the principle of last observation carried forward.
- COVID-19 supplementary analysis: Intercurrent events not related to COVID-19 will be treated as per section 4.2.2.4. Participants who discontinue treatment due to COVID-19 will be treated as missing (hypothetical strategy). Use of rescue therapy for HK due to COVID-19 will be considered to be non-response (composite variable strategy). RAASi down-titration due to COVID-19 (including discontinuation) will be considered to be non-response (composite variable strategy). Participants who die due to COVID-19 will be treated as missing (hypothetical strategy).

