#### **4.2.4.2 Derivations**

Time to first occurrence will be defined as the earliest date of (all-cause hospital admission, ED visits with HK as a contributing factor, all-cause death, use of rescue therapy for HK, date of loss to follow-up, date of 180 days post-discharge) – date of randomization + 1.

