#### **4.2.4.5 Sensitivity Analyses of the Secondary Endpoint #2**

Sensitivity analyses of this secondary endpoint will be performed as per section 4.2.3.5.

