#### **4.2.7 Secondary Endpoint #5 (Hospital admission or ED visit with HK)**

*Time to first occurrence of any component of all-cause hospital admission or ED visit with HK as a contributing factor at any time post-discharge up to 180 days.*

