##### **4.2.7.1 Definition**

- Population: Full analysis set
- Endpoint: Time to first occurrence of either component of the composite outcome at any time post-discharge up to 180 days.
- Intercurrent event strategy: Participants who discontinue treatment or who have hospital admission or ED visit without HK as a contributing factor will continue to be followed up to the first component of the composite endpoint (treatment policy strategy). Participants who die of any cause, use rescue therapy for HK or are lost to follow-up will be censored at the date of death, use of rescue therapy or loss to follow-up respectively. Participants who have RAASI down-titration (including discontinuation) will continue to be followed up to the first component of the composite endpoint (treatment policy strategy). Participants who do not have an event by 180 days post-discharge will be administratively censored at the date of 180 days post-discharge.
- Population level summary (analysis): Kaplan-Meier plots of the survival function for the SZC and SoC treatment groups will be presented. Log-rank test for testing will be used to calculate a two-sided p-value, Cox proportional hazards ratio for estimation, with randomised treatment group (reference level SoC) as the independent variable. The HR and the two-sided 95% confidence interval will be presented. The risk difference and two-sided 95% confidence interval will be presented (as per section 4.2.3.2) at 180 days post-discharge.

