##### **4.2.7.2 Derivations**

Time to first occurrence will be defined as the earliest date of (all-cause hospital admission or ED visit with HK as a contributing factor, all-cause death, use of rescue therapy for HK, date of loss to follow-up, date of 180 days post-discharge) – date of randomization + 1.

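### SAP 4.2.7 and 4.2.7.2 define Secondary #5 with all-cause admissions against its HK-only definition, and Secondary #2 has no rerun past rescue censoring

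*SAP*

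**What the plan says.** **Definition of Secondary #5** (endpoint 4 in protocol 9.4.3.2). SAP Table 5 puts it sixth in the testing order as "Time to first occurrence of hospital admission or ED visit, both with HK as a contributing factor". The overview (SAP 4.2.1, Objective 6) agrees. In SAP 4.2.7.1, participants who "have hospital admission or ED visit without HK as a contributing factor will continue to be followed up". The endpoint statement under the 4.2.7 title, however, reads "Time to first occurrence of any component of all-cause hospital admission or ED visit with HK as a contributing factor", and the derivation in 4.2.7.2 takes the "earliest date of (all-cause hospital admission or ED visit with HK as a contributing factor, all-cause death, use of rescue therapy for HK", followed by loss to follow-up and Day 180.

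**Rescue in #2 and #5.** Both definitions (4.2.4.1, 4.2.7.1) say that participants who die, "use rescue therapy for HK or are lost to follow-up will be censored at the date of death, use of rescue therapy", whichever applies. For #2, "Sensitivity analyses of this secondary endpoint will be performed as per section 4.2.3.5"; 4.2.7.5 says the same for #5. Section 4.2.3.5 contains a covariate-adjusted Cox model, the per protocol set, censoring at RAASi down-titration, and inverse probability weighting for loss to follow-up. For the primary endpoint, by contrast, SAP 4.2.2.5 includes an analysis in which "participants needing rescue therapy for HK will follow the treatment policy strategy".

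**Timing.** The #2 derivation (4.2.4.2) takes the "earliest date of (all-cause hospital admission, ED visits with HK as a contributing factor, all-cause death, use of rescue therapy for HK" and the remaining censoring dates. Neither derivation says whether a participant whose encounter and rescue share a date has an event or is censored.

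**The concern.** Programmers build datasets from the derivation section. If 4.2.7.2 is followed literally, #5 stops at any admission, which 4.2.7.1 forbids. If those stops are coded as events, #5 becomes #2 under another name. Under the fixed sequence in SAP 3.3.4, #5 is formally tested only after #2 has been rejected. A copy of #2 would then pass automatically, and the HK-specific hypothesis would be declared without being tested. If they are coded as censorings, follow-up is lost that the definition says to keep.

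The rescue point is different in kind. Protocol 6.7.1 ties rescue to severe HK, and protocol 2.1 links HK severity to admissions. People censored at rescue may therefore be at higher risk of the encounter being counted, and perhaps to a different extent in each arm. Censoring at rescue is a legitimate prespecified choice, but nothing planned shows how far the hazard ratio of #2 depends on it.

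**Working it through.** **1. The #5 passages side by side**

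| Place | Admissions that count |
|---|---|
| SAP Table 5, order 6 | HK only |
| SAP 4.2.1, Objective 6 | HK only |
| SAP 4.2.7.1 | components not listed; follow-up continues past non-HK admissions |
| Protocol Table 3 and 9.4.3.2, endpoint 4 | HK only |
| SAP 4.2.7, endpoint statement | all-cause |
| SAP 4.2.7.2, derivation | all-cause |

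The 4.2.7 statement is word for word the one that opens 4.2.4 for #2, and the 4.2.7.2 list of dates has the same content as 4.2.4.2. Both endpoints are analysed as in 4.2.3.4. If the stops are coded as events, the same data go into the same log-rank test.

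**2. The plan's own sizing figure.** Protocol 9.2.2 sizes Secondary #1; no size is given for #2 or #5.
- HR = ln(0.83)/ln(0.568) = 0.329.
- Freedman events = (1.960 + 0.842)² × (1.329/0.671)² = 30.8, so 31.
- 31/((0.17 + 0.432)/2) = 103, so 52 per arm. This reproduces the protocol.

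The 17% and 43.2% are sums of all-cause hospitalisation (16.2%, 40%) and HK ED visits (0.8%, 3.2%). Those are the components of #2, so the rates can be borrowed here.

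**3. Size of the wording conflict, 52 per arm**
- All-cause admissions: 0.40 × 52 = 20.8 SoC; 0.162 × 52 = 8.4 SZC.
- HK ED visits: 0.032 × 52 = 1.7; 0.008 × 52 = 0.4.
- Events if every admission counts: 52 × (0.432 + 0.17) = 31.3.
- Let h be the share of admissions that are HK-related. The documents do not give it; assume 5-25%. HK-only events = 52 × (0.40h + 0.032) + 52 × (0.162h + 0.008) = 3.5 at h = 0.05 and 9.4 at h = 0.25.
- Participants with a non-HK admission: 20.8 × (0.75 to 0.95) = 15.6-19.8 SoC and 8.4 × (0.75 to 0.95) = 6.3-8.0 SZC, or 21.9-27.8 of 104. At these admissions 4.2.7.2 stops the clock and 4.2.7.1 does not.

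**4. Same-date rescue.** The earliest-date rule fixes the time but not the status. The rescue list in protocol 6.7.1 includes acute treatments that could be given at the encounter itself. If 25-50% of #5 events had rescue on the same date (assumed), between 0.25 × 3.5 = 0.9 and 0.50 × 9.4 = 4.7 events could be coded as censored.

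**5. What follows past rescue**
- Counts #3 and #6 (SAP 4.2.5.1, 4.2.8.1): yes, by negative binomial regression.
- Exploratory #1, #2 and #3 (4.2.9.1, 4.2.10.1, 4.2.11.1): yes, by log-rank/Cox on HK encounters plus death.
- Exploratory #13 (4.2.21.1): yes, but all ED and outpatient visits count.
- Time to first event in #2 or #5: no.
- The reverse Kaplan-Meier (4.2.3.4) pools rescue with every other reason for censoring.

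**6. Can the effect of rescue censoring on the HR be signed?** Illustration only. Event risks are 17% and 43.2%, times are exponential, and event and rescue share a gamma frailty of variance v. The hazard is multiplied by m after rescue. Rescue rates, v and m are all assumed; HRs come from large simulated samples.

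| Rescue SoC/SZC | v | m | HR past rescue | HR censored |
|---|---|---|---|---|
| 30%/5% | 0 | 1 | 0.331 | 0.331 |
| 30%/5% | 1 | 1 | 0.327 | 0.357 |
| 30%/30% | 3 | 1 | 0.318 | 0.253 |
| 30%/5% | 0 | 0.33 in Arm B | 0.368 | 0.327 |

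The censored HR can equal, exceed or fall below the follow-through HR. These rows are not bounds.

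**The case against.** On #5, Table 5, the overview, 4.2.7.1 and the protocol all agree, and the 4.2.7 wording would make #5 redundant. The two passages look like text carried over from #2, not an open question about the endpoint. That is right, and a reader should not infer that the intended definition is in doubt. The derivation is still wrong as written, and it is the part that gets coded.

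On rescue, the censoring is explicit and the same in both documents, and a reader might wrongly infer that nothing is planned past rescue. Exploratory #1 is the components of #5 plus death, and the protocol synopsis regards death without prior hospitalisation or ED visit as negligible. It is therefore a close proxy for a #5 rerun, though not identical, since deaths after non-HK admissions count. This moves the gap mainly to #2. There, count #3 answers a rate question and Exploratory #13 is a much broader endpoint.

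The missing strategy name for rescue changes no number. A reader might also infer that the protocol contradicts itself on when a binder counts as rescue. Protocol 6.2 and 6.7.1 show no actual conflict, and final classification belongs to the adjudication committee under a charter that is not among the documents.

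**Conclusion.** The Secondary #5 endpoint statement and derivation contradict its definition and need correcting; this rests on the text alone. The 21.9-27.8 participants affected, against 3.5-9.4 HK events, rest on the protocol's planning rates and an assumed 5-25% HK share. The same-date rule is a smaller missing detail in the same derivations.

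The absent rerun past rescue is a cheap robustness gap, mainly for #2. It is tempting to infer that the planned HR is biased in a known direction, or that power is lost. The documents do not support either, because they give no rescue rate and no effect of rescue on later risk, and the illustrations go both ways. For the same reason it cannot be said that the effect is small.

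**What to change.** 1. In SAP 4.2.7 (endpoint statement) and 4.2.7.2, replace the all-cause wording with that of Table 5: "Time to first occurrence of hospital admission or ED visit, both with HK as a contributing factor".
2. In 4.2.4.2 and 4.2.7.2, state that a qualifying admission or ED visit on the same date as rescue counts as the event.
3. In 4.2.4.5 and, for symmetry, 4.2.7.5, add a treatment-policy log-rank/Cox analysis that follows past rescue to Day 180, reported beside the planned one.
4. Optional wording: name the strategy for rescue in 4.2.4.1 and 4.2.7.1, since protocol 9.4.1 adopts that language.

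The cost is SAP text and one extra run per endpoint, settled before database lock. No new data are needed. Encounters are collected at every outpatient visit (protocol Table 1), participants who stop study drug are still followed (7.1.1), and rescue date and time are recorded (6.7.1). SAP 4.2.5.3 and 4.2.8.3 already use encounters regardless of intercurrent events. The downside is that the added estimate includes the effect of binders started as rescue in Arm B, possibly SZC itself, which can pull the HR toward 1. It should therefore sit alongside the planned analysis and not replace it.

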#### **4.2.4.2 Derivations**

Time to first occurrence will be defined as the earliest date of (all-cause hospital admission, ED visits with HK as a contributing factor, all-cause death, use of rescue therapy for HK, date of loss to follow-up, date of 180 days post-discharge) – date of randomization + 1.

#### **4.2.4.3 Handling of Dropouts and Missing Data**

Participants who are lost to follow-up will be censored at the date of discontinuation as recorded on the participant's disposition form.

#### **4.2.4.4 Primary Analysis of Secondary Endpoint #2**

The primary analysis of this secondary endpoint will be performed as per section 4.2.3.4.

#### **4.2.4.5 Sensitivity Analyses of the Secondary Endpoint #2**

Sensitivity analyses of this secondary endpoint will be performed as per section 4.2.3.5.

#### **4.2.4.6 Supplementary Analyses of the Secondary Endpoint #2**

Not Applicable.

#### **4.2.4.7 Subgroup Analyses**

Subgroup analyses will be performed using separate Cox models, as per section 4.2.3.4, by presence of heart failure (Yes/No, identified per Medical History using an SMQ of "Cardiac Failure"; SMQ Code: 20000004), RAASi use at screening (Yes/No, identified per Concomitant Medication eCRF as CMCLASCD in ('C09AA', 'C09BA', 'C09BB', 'C09BX', 'C09CA', 'C09DA', 'C09DB', 'C09DX', 'C09XA') where Start Date is prior to date of informed consent), CKD stage, without diagnosis of CKD (but eGFR <90), baseline K+ (5.0 < K+ ≤ 5.5 versus 5.5 < K+ ≤ 6.5 mmol/L) and an alternative baseline K+ categorisation (5.0 < K+ ≤ 5.5, 5.5 < K+ ≤ 6.0, and 6.0 < K+ ≤ 6.5 mmol/L) at baseline. Subgroup analyses will only be conducted providing there are 10 or more events per subgroup category.

### **4.2.5 Secondary Endpoint #3 (Number of all-cause hospital admissions or ED visits with HK)**

*Number of all-cause hospital admissions or ED visits with HK as a contributing factor, at any time post-discharge up to 180 days.*

#### **4.2.5.1 Definition**

- Population: Full analysis set
- Endpoint: Number of all-cause hospital admissions or ED visits with HK as a contributing factor at any time post-discharge up to 180 days.
- Intercurrent event strategy: Participants who discontinue treatment, use rescue therapy for HK or who have an ED visit without HK as a contributing factor, will continue to be followed up to the first component of the composite endpoint (treatment policy

strategy). Participants who die of any cause or are lost to follow-up will be censored at the date of death or loss to follow-up. Participants who have RAASi down-titration (including discontinuation) will continue to be followed up to the first component of the composite endpoint (treatment policy strategy).

- Population level summary (analysis): Mean number of all-cause hospital admissions or ED visits, with HK as a contributing factor by randomised treatment group. Negative binomial regression model with randomised treatment group as the independent variable and including duration of time in study as an offset. The incidence rate (SZC/SoC), along with 95% confidence intervals and two-sided p-values will be displayed.

#### **4.2.5.2 Derivations**

For each participant the total number of separate all-cause hospital admissions or ED visits with HK as a contributing factor up to 180 days will be calculated. Hospital admissions and ED visits will be calculated as separate admissions if start and stop dates of admission do not overlap. If hospital admissions or ED visits are missing a start, stop date or both then they will be calculated as separate admissions. Hospital admissions or ED visits started after 180 days will not be counted.

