5.1 Inclusion Criteria

Participants are eligible to be included in the study only if all of the following criteria apply:

Age

- 1 Must be 18 years of age or older, at the time of signing the informed consent

Type of Participant and Disease Characteristics

- 2 Admitted to hospital (inpatient care; directly or from ED)
- 3 With:
 - Diagnosed CKD (any stage)
 - or
 - eGFR $< 90 \text{ mL/min/1.73 m}^2$ at, or within 3 months of, study screening, based on the Chronic Kidney Disease Epidemiology Collaboration (CKD-EPI) equation ([Levey et al, 2009](#)). Note: Race/ethnicity should not be included in CKD-EPI equation calculation.
- 4 Local laboratory K^+ measurement within 24 hours of baseline visit (visit 2), where result is either:
 - Hyperkalaemic as defined by site's local practice and $\text{K}^+ \leq 6.5 \text{ mmol/L}$
 - Or, normokalaemic: K^+ between ≥ 3.5 and $\leq 5.0 \text{ mmol/L}$, where patient started and is receiving treatment for this episode of HK.

Sex

- 5 Male or female

Informed Consent

- 6 Capable and willing of giving signed informed consent as described in [Appendix A](#) which includes compliance with the requirements and restrictions listed in the informed consent form (ICF) and in this protocol.

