### **3.3.1.3 Handling of missing dates**

Incomplete dates (partial or missing dates where a full date is permissible) will be presented in the data listings as recorded on the eCRF. Missing hospital admission, emergency department and death dates will not be imputed. Every effort will be made to ensure complete information for these dates are available. However, for adverse event start and stop date and for prior and concomitant medication start and stop date, missing dates will be estimated as follows:

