##### **4.2.8.2 Derivations**

For each participant the total number of separate hospital admissions or ED visits with HK as a contributing factor up to 180 days will be calculated. Hospital admissions and ED visits will be calculated as separate admissions if start and stop dates of admission do not overlap. If hospital admissions or ED visits are missing a start, stop date or both then they

will be calculated as separate admissions. Hospital admissions or ED visits started after 180 days will not be counted.

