#### **4.2.14.2 Derivations**

For each participants the total number of separate hospital admissions with HK as a contributing factor up to 180 days will be calculated. Hospital admissions will be calculated as separate admissions if start and stop dates of admission do not overlap. If hospital admissions are missing a start, stop date or both then they will be calculated as separate admissions. Hospital admissions after 180 days will not be counted.

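### The count rule for secondary #3 and #6 ignores a known start date when a stop date is missing, so one HK ED-to-ward episode can score two events; at the planning rates the effect on #3 is small

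*SAP*

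**What the plan says.** Secondary #3 (SAP numbering) is defined in SAP 4.2.5.1: "Number of all-cause hospital admissions or ED visits with HK as a contributing factor at any time post-discharge up to 180 days." Admissions count whatever the cause; ED visits count only if HK contributed. Secondary #6 restricts both to HK.

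SAP 4.2.5.2 sets the counting rule in two sentences. The first deals with dated records: "Hospital admissions and ED visits will be calculated as separate admissions if start and stop dates of admission do not overlap." By implication, overlapping records form one event. The second deals with undated records: "If hospital admissions or ED visits are missing a start, stop date or both then they will be calculated as separate admissions." SAP 4.2.8.2 has the same pair of sentences for #6. SAP 4.2.14.2 has the admissions-only form for exploratory #6: "If hospital admissions are missing a start, stop date or both then they will be calculated as separate admissions."

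SAP 3.3.1.3 adds: "Missing hospital admission, emergency department and death dates will not be imputed", followed by "Every effort will be made to ensure complete information for these dates are available."

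SAP Table 5 places #3 and #6 at orders 4 and 7 of the testing hierarchy. Of the three sensitivity analyses in SAP 4.2.5.5 (covariate-adjusted model, mean cumulative count, per protocol set), none varies the merging rule.

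**The concern.** The first sentence treats a visit that runs from the ED to the ward as one event. The second withdraws that whenever either record lacks a stop date, even if both start dates are known. Take an HK ED visit starting on 3 March with no stop date, and an admission starting on 3 March. With complete dates this scores 1; with the ED stop date missing it scores 2. The start dates alone are enough to link the records.

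Cleaning cannot remove every case. An admission still open at last contact has no stop date to find. Protocol 8.8.1 relies on asking participants about encounters and, where needed, requesting records from hospitals that do not share an electronic record, so some ED stop times may never be obtained.

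In #3 an ED-to-ward duplicate requires an HK ED visit, because other ED visits do not count. The problem is not confined to HK, however: two admission records for one stay, such as a transfer, would also score 2 in #3 for any cause if a date were missing. What is at stake is the rate ratio and its precision in two formally tested counts. The time-to-first endpoints are untouched, because a duplicate record does not change the date of the first event.

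**Working it through.** **The plan's own figures.** Protocol 9.2.2 assumes 6-month all-cause hospitalisation of 16.2% (SZC) and 40% (SoC), and HK ED visits of 0.8% and 3.2%. It adds them: 16.2 + 0.8 = 17% and 40 + 3.2 = 43.2%. The hazard ratio follows: ln(0.83)/ln(0.568) = 0.329. Freedman's formula gives 7.849 × (1.329/0.671)² = 30.8, so 31 events; 31/0.301 = 103, or 52 per arm, as stated. Randomised: 104/0.8 = 130, or 65 per arm. The plan gives no figure for the counts in #3 or #6.

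**Secondary #3, ED figures read as all HK ED visits.** Let w be the share of HK ED visits that lead to admission and m the share of those pairs with a missing date. Neither is in the documents. Taking one event per affected participant:

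- Episodes counted once: IRR = [0.162 + 0.008(1 − w)] / [0.40 + 0.032(1 − w)]
- SAP rule: add 0.008wm to the numerator and 0.032wm to the denominator.

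| w | m | IRR, counted once | IRR, SAP rule | Change |
|---|---|---|---|---|
| 1 | 10% | 0.405 | 0.404 | −0.3% |
| 1 | 20% | 0.405 | 0.403 | −0.6% |
| 1 | 50% | 0.405 | 0.399 | −1.5% |
| 1 | 100% | 0.405 | 0.394 | −2.8% |
| 0.5 | 100% | 0.399 | 0.394 | −1.4% |

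At w = m = 1 the extra counts are 65 × 0.032 = 2.1 in SoC and 65 × 0.008 = 0.5 in SZC, so 3.2/(3.2 + 0.8) = 80% of them fall in SoC. For scale, 26 and 10.5 admissions (65 × 0.40 and 65 × 0.162) give a Poisson standard error of the log ratio of √(1/26 + 1/10.5) = 0.37. The largest shift, ln(0.394/0.405) = −0.03, is under a tenth of that.

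**Secondary #3, ED figures read as visits without admission.** The simple addition in Protocol 9.2.2 also allows this reading. ED-to-ward pairs are then extra, and their shares of admissions (hA in SZC, hB in SoC) are assumptions. The IRR counted once is 0.170/0.432 = 0.394; under the SAP rule it is (0.170 + 0.162·hA·m)/(0.432 + 0.40·hB·m).

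| hB | hA | m = 10% | m = 100% |
|---|---|---|---|
| 10% | 5% | 0.392 (−0.4%) | 0.377 (−4.1%) |
| 30% | 10% | 0.387 (−1.8%) | 0.337 (−14.3%) |
| 10% | 10% | 0.394 (0.0%) | 0.394 (+0.2%) |

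A large shift needs a high share of admissions through an HK ED visit, a clear arm difference in that share, and widespread missing dates.

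**Secondary #6.** If a fraction q of HK episodes is duplicated, each arm's rate is multiplied by (1 + q). With equal q the factor cancels: a ratio of 0.25 stays 0.25. With unequal q the ratio is multiplied by (1 + qA)/(1 + qB); for example, an assumed 5% v 10% gives 1.05/1.10 = 0.955. Precision can still suffer. If a random fraction d of Poisson events is doubled, the variance of the log rate is multiplied by (1 + 3d)/(1 + d)², at most 1.125 at d = 1/3, which raises the standard error by 6%.

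**The case against.** The other side has four good points.

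- Double counting needs two records and a missing date. SAP 3.3.1.3 commits to completing these dates. Hospitalisation is also a seriousness criterion (Protocol Appendix B 2), and Protocol 8.3.2 collects admission and discharge dates for serious adverse events. The case report form is not among the documents, so it is unknown whether an ED visit ending in admission gets its own record.
- The rule is prespecified and the same in both arms, and HK classification is blinded (SAP 4.2).
- On the first reading of Protocol 9.2.2, HK ED visits can account for at most 3.2/40 = 8% of SoC admissions and 0.8/16.2 = 4.9% of SZC admissions, so the effect on #3 is slight.
- A careless repair could do more harm than the rule does. If every missing admission stop date were set to Day 180, one undated admission on Day 10 would absorb all later events.

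All four stand as limits on size and on the remedy. They do not remove the defect: cleaning is an aim rather than an analysis rule, and it cannot supply a stop date for a stay that is still open.

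A reader might infer more: that ED-to-ward episodes are routinely counted twice, mostly in SoC, so that both rate ratios are materially biased towards SZC. The documents do not support this. They give no rate of missing dates and no difference in missingness by arm. The excess in SoC is an inference from the planning rates. In #6, more duplicates in the arm with more episodes is not in itself bias.

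**Conclusion.** The rule as written can give a wrong count in #3 and #6 (and, for admissions, in exploratory #6), because it discards start dates that would link records. Nothing else in the plan corrects or tests this.

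The expected size for #3 is small: from 0.405 to 0.404 with 10% of dates missing, and to 0.394 with all missing. This assumes that every HK ED visit leads to admission, that the planning ED rates cover all HK ED visits, and that each affected participant has one event. If those rates exclude visits ending in admission, the documents set no ceiling. The shift could then be larger, and its direction would depend on whether the share of admissions arriving through an HK ED visit is higher in SoC. These figures cover ED-to-ward pairs only; duplicated admission records cannot be sized from the documents. The #6 ratio is biased only if duplication per HK episode differs by arm.

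The case for changing the rule is that a formally tested count should not depend on whether a stop date was recorded, and that the change is cheap.

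**What to change.** Amend SAP 4.2.5.2 and 4.2.8.2, with the admission parts carried into 4.2.14.2, before database lock:

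1. Where an ED start date is known and the stop date is missing, set the stop date to the start date.
2. Count as one event, even if a stop date is missing: an ED visit and an admission that start on the same day; two admission records that start on the same day; and a record that starts within another record's known dates.
3. Treat an admission as open until last contact, death or Day 180 only when it is documented as ongoing then. Impute no other missing admission stop date.
4. Keep the separate rule only where the start date is unknown or no link can be shown.
5. Amend the no-imputation sentence in SAP 3.3.1.3 to match.
6. Report the number of undated records by arm, including those with no start date, which cannot be placed against the 180-day limit.

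The cost is SAP wording and a few lines of programming. The downside is that a true second encounter on the same day would be merged. An ED visit with no stop date that starts the evening before an admission would still count separately, unless the two can be linked from the records.
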